15.0 Risks to Subjects

The risks to the subjects are minimal. The anesthetics will be standard of care and the BSS and povidone-iodine ophthalmic solutions are commonly used eye surgery solutions that are safe for the application to the ocular surface in the manner in which we propose, as deemed by the FDA. These solutions are routinely used during strabismus surgery. As stated previously, the duration of the study intervention is very brief (seconds, to 4 minutes) and will cause minimal, if any, delay in the surgical procedure. If apnea becomes significant (e.g. arterial oxygenation saturation less than 94%, as measured by pulse oximetry), assisted or controlled ventilation is very easily provided via the LMA to counteract the apnea.

There is a risk of loss of confidentiality, but the anesthesia research team has safeguards in place for keeping patient health information secure and only accessed when absolutely necessary. All data will be stored on a secure server and consent and data forms will be held in a locked cabinet in a locked research office.

Though it is a randomized study, there is not a risk of randomization because neither of the possible groups poses any additional risk to the participants.

16.0 Potential Benefits to Subjects or Others

There is no direct benefit to participants by being enrolled in this research study, but the information gained from completing this study may enable pediatric anesthesiologists to predict when respiratory changes may occur during the course of strabismus surgery. Subsequent studies, based on the findings of this study may determine whether pretreatment with glycopyrrolate or atropine may attenuate or prevent changes in respiration.

Title: *The Effect of Povidone-iodine Ophthalmic Surgical Prep Solution on Respiration in Children Undergoing Strabismus Surgery with General Anesthesia*

NCT03349515

2018 August 15

Statistical Analysis: An *a priori* size calculation was conducted prior to the study. Assuming no change in the peak to peak end-tidal CO₂ interval time after drop instillation in the saline group, and a peak to peak interval time variability of ± 4 seconds, a sample size of 50 patients per group (100 patients total) provided $> 80\%$ power to detect an increase in change in peak to peak interval of 2.5 seconds in the povidone-iodine group compared to the saline group assuming equal variance between the two groups using a 2-sided test with significance level at $\alpha=0.05$.

Descriptive statistics by treatment group were estimated for patient and procedural characteristics. Differences in peak to peak interval time between the saline and povidone-iodine exposure groups were examined using a linear mixed model approach. Based on the *a priori* analysis plan, the model included fixed effects for treatment, breath number, a treatment by breath number interaction and a random subject effect to account for correlation between measures collected on the same subject. The model also controlled for factors thought to be associated with respiratory rate including age, pre-term birth, history of apnea, and breath duration prior to drop installation. Comparisons in breath duration between treatment groups at each of 15 breaths post-drop instillation were estimated from the model using Bonferroni corrected significance.

A secondary outcome of interest was occurrence of a significant change in respiration. Although apnea has been defined in the literature as a breath duration of 10 to 20 seconds, this definition is arbitrary and fails to account for within and between subject variability of breath duration. To account for within and between subject variability, we defined changes in respiration as having a breath duration greater than twice the inner-quartile range above the

75th percentile for breaths within patient for the 10 breaths prior to and 15 breaths after instillation of drops. Associations between occurrence of change in respiration with patient and procedural characteristics were evaluated using univariate logistic regression models. Notably, no participants in the saline group experienced a change in respiration; therefore, all additional univariate tests were conducted on the subset of patients that received povidone-iodine drops. All analyses were conducted in SAS v.9.4 (SAS Institute, Cary NC, USA).

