for 5 breaths. Specifically, at the patient's peak inspiration (as seen on the capnography), the study member will start the stopwatch and proceed to hit the 'lap' button for the next 5 consecutive inspiration peaks. These data intervals will be recorded on the data sheet after the 5 breaths are over, as the intervals are conveniently stored and numbered below the stopwatch in the app. We will do this to establish an average baseline respiratory rate for each individual patient. Next, patients who are randomized to Group A will receive three drops of povidone-iodine ophthalmic solution in each eye, with the right eye to receive the drops first. Group B will receive three drops in each eye of ophthalmic balanced salt solution. Similarly, the right eye will receive the drops first; the reason being that we know that there are differences in sympathetic stimulation on the right side of the face vs left (e.g. termination of supraventricular tachycardia) and although we don't know if this effects OCR, we chose to standardize right eye first. The eye drops will be administered by the study anesthesiologist. After application of either solution to the eyes of the patient, any change in ventilation can be detected and timed by observation of the capnography (end-tidal carbon dioxide) and direct observation of the chest wall with use of the iPhone stopwatch feature again. The capnograph is a standard monitor of respiration used during the administration of general anesthesia. Data collected at this time will include whether or not there was a change in respiration, what this change in respiration was, if assisted ventilation was required, how long assisted ventilation was required (if applicable), HR, BP, RR, SaO_2 , ETCO_2 , InspSevo, and ExpSevo. This study intervention and data collection will take less than 5 minutes and the surgical team will then progress with the case as they normally would.

Other data to be collected is as follows:

- Attending anesthesiologist and CRNA
- Age
- Weight
- Sex
- Co-existing diseases
- If the patient was a pre-term birth and if yes, the estimated gestational age at birth
- If premedication was given and if yes, what medication and dose
- If N_2O was used during inhalational induction

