12.0 Data Management

Descriptive statistics by treatment group will be evaluated for all demographic and procedural characteristics. The goal of the study is to determine if there is a significant difference in the change in respiratory response immediately following administration of saline or povidone-iodine solution in patients undergoing strabismus surgery. The primary outcome is the difference between the peak to peak interval time from the capnograph measured before saline or povidone-iodine administration versus after administration. Pre-exposure peak to peak interval will be measured as the average time between peaks for five breaths prior to administration. Post-exposure peak to peak interval will only be evaluated as the time between the two peaks at saline or povidone-iodine administration. Differences in the change in peak to peak interval time between the saline and povidone-iodine exposure groups will be evaluated using a linear regression approach. The model will include a treatment effect and will additionally control for patient age, history of prematurity, and use of any pre-medication to account for other factors thought to be associated with respiratory rate. We anticipate no change in peak to peak interval time in the saline group with variability of ± 4 seconds. A sample size of 50 patients per treatment group (100 patients total) provides $>80\%$ power to detect an increase in change in peak to peak interval of 2.5 seconds in the povidone-iodine group compared to the saline group assuming equal variance between the two groups using a 2-sided test with significance level set at alpha = 0.05. If the variability of the povidone-iodine group is larger, for example a variability of 8 seconds, compared to 4 seconds in the saline groups we still have 80% power to detect an increase in the povidone-iodine group of approximately 4 seconds.

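### The SAP attributes its 15-breath mixed model to an *a priori* plan, but the supplied protocol plans a one-interval linear regression, and the difference is neither dated nor explained

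*SAP*

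**What the plan says.** **Protocol, section 12.0 (Data Management).** The primary outcome is the before-to-after difference in capnograph peak-to-peak interval. The baseline is defined thus: "Pre-exposure peak to peak interval will be measured as the average time between peaks for five breaths prior to administration". The post-drop value is a single interval: "Post-exposure peak to peak interval will only be evaluated as the time between the two peaks at saline or povidone-iodine administration". Differences between arms in this change "will be evaluated using a linear regression approach", with a treatment effect, and the model will additionally "control for patient age, history of prematurity, and use of any pre-medication". The sample size is based on a two-sided test at alpha 0.05.

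**Protocol, section 10.0 (Study Design / Methods).** The five-breath baseline is timed with a stopwatch lapped "for the next 5 consecutive inspiration peaks". Both arms receive three drops per eye, one eye after the other, "with the right eye to receive the drops first". The data to be collected include "If premedication was given and if yes, what medication and dose".

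**SAP, Statistical Analysis.** A linear mixed model is described: "Based on the *a priori* analysis plan, the model included fixed effects for treatment, breath number, a treatment by breath number interaction", plus a random subject effect. The covariates named are age, pre-term birth, history of apnea and pre-drop breath duration. Arms are compared at each of 15 post-drop breaths with Bonferroni correction. The power statement for 50 per group is the protocol's. The text is in the past tense and reports that no saline participant had a change in respiration.

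**The concern.** A reader who meets the words *a priori* will take the 15-breath mixed model as the prespecified primary analysis and see nothing to check. In the supplied protocol the prespecified analysis has a different outcome window, model and number of tests, and a partly different covariate list.

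The SAP does not describe the section 12.0 regression at all. Its result cannot be identified, and a reader cannot tell whether the primary analysis was replaced, when, or why. The SAP already contains an outcome by arm, so it cannot itself be the advance plan it refers to. The claim of prespecification needs a dated source, and none is cited.

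A smaller consequence concerns power. The SAP sets the protocol's power figure beside an analysis to which it does not apply.

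**Working it through.** **Step 1. The two plans side by side.**

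| Element | Protocol section 12.0 | SAP |
|---|---|---|
| Post-drop data | One interval, at administration | 15 breaths |
| Response | Change from five-breath mean | Breath duration, with pre-drop duration as a covariate (number of breaths not stated) |
| Model | Linear regression with treatment effect | Linear mixed model: treatment, breath number, interaction, random subject effect |
| Covariates in both | Age, prematurity | Age, pre-term birth |
| Covariates in one | Any pre-medication | History of apnea, pre-drop breath duration |
| Testing | One two-sided test, alpha 0.05 | 15 contrasts, Bonferroni-corrected |

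Section 12.0 says the post-exposure interval will only be evaluated at administration. That restriction excludes a 15-breath window, so the mixed model is not a fuller account of the same plan. The SAP's covariate list is introduced by the word *including*, so the absence of pre-medication may be incomplete reporting.

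**Step 2. Dates and reasons.** The SAP's only date is its heading, 15 August 2018, which dates the document and not a change of analysis. The SAP gives a reason for its secondary definition of a change in respiration (variability within and between subjects). It gives none for the primary model.

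**Step 3. The stated power.** Inputs from section 12.0, repeated in the SAP: difference 2.5 s, variability 4 s (read here as the SD of the change), 50 per group, two-sided alpha 0.05.

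- Standard error = 4 × √(2/50) = 0.80 s.
- Standardized difference = 2.5 / 0.80 = 3.125.
- Normal approximation: Φ(3.125 − 1.960) = Φ(1.165) = 0.878. Noncentral t: 0.872.

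The figure of more than 80% is therefore reproduced, for one comparison of one change.

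**Step 4. The same inputs for one of the 15 contrasts (illustration only).**

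- Bonferroni level = 0.05/15 = 0.0033, critical value about 2.935.
- Normal approximation: Φ(3.125 − 2.935) = Φ(0.190) = 0.575. Noncentral t: 0.548.

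This assumes an SD of 4 s at each breath and no precision gained from covariates or repeated measures. It is not the power of the overall treatment or interaction test, which cannot be computed from the documents.

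**The case against.** The strongest reply is that an earlier plan may exist outside the supplied documents. The protocol text carries no date or version, and its section numbers run from 10.0 to 12.0. This stands. The finding is that the supplied protocol does not support the attribution, not that the attribution is false. If a dated plan is produced, ranking the mixed model as secondary would be wrong, so that step must be conditional.

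A second reply is that the protocol is broader than section 12.0. Section 4.0 states the endpoint as any respiratory effect, specifically a change in rate, and section 10.0 plans to detect and time changes in ventilation after the drops. Following several breaths is therefore not foreign to the study. But these sections describe what is observed. Section 12.0 defines the primary measure and model, and limits the measure to one interval.

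A third reply is that the mixed model is a reasonable analysis. Adjusting for pre-drop duration is a defensible alternative to a change score, and Bonferroni correction limits false positives across the 15 contrasts. Both points are right. Neither makes it the planned analysis.

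Some stronger readings are tempting but not supported:

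- **That leaving out pre-medication biases the result.** Treatment was randomized, so omission would not by itself bias the comparison, and the list may be incomplete.
- **That the SAP's 10 pre-drop breaths contradict the protocol's five.** The 10 belong to a within-patient rule for a secondary outcome and can coexist with a five-breath primary baseline.
- **That the trial's power claim is wrong.** The SAP presents it as an advance calculation for the change at alpha 0.05 and does not claim it for the 15 contrasts.

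**Conclusion.** The concern holds as a discrepancy between the SAP's statement of prespecification and the only prospective plan supplied. Its size is one planned test (one post-drop interval, five-breath baseline, alpha 0.05) against 15 contrasts at 0.0033, with a different model and a partly different covariate list, and with no date or reason given.

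A reader might infer that the mixed model was chosen after the results were seen. The documents do not show that. They show that the SAP text was written with a by-arm result known, which is why a dated source matters. They do not show when the model was chosen.

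The contradiction is one of text and does not depend on any calculation. The power figures (87% for the planned test, about 55% for one corrected contrast) rest on reading 4 s as an SD and only show that the stated figure belongs to the single-interval test.

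If a dated plan can be produced, this is a reporting gap that should be closed. If not, it must be fixed, because it concerns which analysis is primary.

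**What to change.** **If a dated plan exists:** cite the plan that specifies the 15-breath mixed model, show that it predates access to outcome data, and explain why it differs from section 12.0.

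**If it does not:** remove *a priori* from the mixed-model sentence and disclose the departure with its date and reason. Report the section 12.0 regression as the primary analysis (five-breath baseline; age, prematurity and any pre-medication; alpha 0.05), and label the mixed model secondary.

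**In either case:**

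- Report the section 12.0 regression.
- Define the interval at administration. Section 12.0 does not say which one it is when two eyes are treated in sequence. Take the definition from study records made before results were known, if there are any. Otherwise disclose that it was set afterwards, apply the same rule in both arms, and show the result under each reasonable reading.
- State that the power above 80% refers to the single-interval test at alpha 0.05 and not to the 15 corrected contrasts.

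**Cost:** one regression, possibly repeated under alternative interval definitions, and changes to the SAP's wording; no new patients. There are two real downsides. The 15-breath result may become supportive, and the interval definition may have to be made after results are known, which is why the alternatives should be shown.

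### The SAP names no residual variance structure; fitted as written, its mixed model understates the standard error at a breath where responses concentrate

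*SAP*

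**What the plan says.** The SAP's Statistical Analysis text describes a linear mixed model: "the model included fixed effects for treatment, breath number, a treatment by breath number interaction", together with "a random subject effect to account for correlation between measures collected on the same subject". It adjusts for factors "including age, pre-term birth, history of apnea, and breath duration prior to drop installation". It then states: "Comparisons in breath duration between treatment groups at each of 15 breaths post-drop instillation were estimated from the model using Bonferroni corrected significance". Nothing is said about the residual covariance, about variances differing by breath or arm, or about empirical standard errors.

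Two other places bear on whether one common variance is reasonable.

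- Protocol section 12.0 bases its main power figure on equal variances, then considers a larger spread after povidone-iodine, "for example a variability of 8 seconds, compared to 4 seconds in the saline groups". The SAP repeats only the equal-variance case. The protocol's outcome is a single interval: "Post-exposure peak to peak interval will only be evaluated as the time between the two peaks at saline or povidone-iodine administration".
- The SAP's secondary outcome counts a child as having a change in respiration if a breath lies more than twice the interquartile range above that child's own 75th percentile over 25 breaths (10 before the drops, 15 after). It reports that "no participants in the saline group experienced a change in respiration".

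**The concern.** A random subject effect with nothing else specified ordinarily means one residual variance for all 15 breaths and both arms. The standard error at any breath is then built from the average variance over all 30 breath-by-arm cells. A pause after the drops in some povidone-iodine children, but not in saline children, raises the variance in one of those cells. Averaging over the 29 quieter cells hides that increase at the breath where the effect lies.

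That breath's contrast is the one that answers the trial's question, and its interval and p-value would look more precise than they are. Bonferroni does not help, because it moves the threshold and leaves the standard error alone. The protocol's single-interval regression does not pool over breaths and is not exposed to this.

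**Working it through.** **1. The plan's own figures.** With 50 per arm and SD 4 s, SE = 4 × √(2/50) = 0.80 s. Power for 2.5 s at two-sided 0.05 is 87.8% (normal) or 87.2% (noncentral t), so the stated figure of more than 80% is right. With 8 versus 4 s, SE = √((64 + 16)/50) = 1.265 s. The difference detectable with 80% power is 2.80 × 1.265 = 3.54 s, consistent with the protocol's approximate 4 s.

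**2. Inputs for the check.** From the documents: 50 per arm, 15 breaths, SDs of 8 and 4 s, Bonferroni level 0.05/15 = 0.0033 (critical z = 2.935). Assumed: 8 versus 4 s are residual SDs at one response breath, the other 28 cells have SD 4 s, and the between-child SD (sb) is 0, 2 or 4 s. The documents give no per-breath SDs.

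**3. Formulas (balanced data, no covariates).**

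- Pooled residual variance = (64 + 16 + 28 × 16)/30 = 17.6.
- Model SE = √(2(sb² + 17.6)/50).
- True SE at the response breath = √((2sb² + 80)/50).
- Coverage of a nominal 95% interval = 2Φ(1.96 × model SE / true SE) − 1.
- Smallest difference reaching 0.0033 = 2.935 × SE.

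| | sb = 0 | sb = 2 | sb = 4 |
|---|---|---|---|
| Model SE (s) | 0.839 | 0.930 | 1.159 |
| True SE (s) | 1.265 | 1.327 | 1.497 |
| SE too small by | 34% | 30% | 23% |
| Coverage of 95% interval | 80.6% | 83.0% | 87.1% |
| Smallest difference passing, model SE (s) | 2.5 | 2.7 | 3.4 |
| Smallest difference passing, true SE (s) | 3.7 | 3.9 | 4.4 |
| p for an observed 3.0 s, model SE | 0.00035 | 0.00125 | 0.0097 |
| p for an observed 3.0 s, true SE | 0.018 | 0.024 | 0.045 |

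At the quiet breaths the model SE is slightly too large (0.839 against 0.800 s at sb = 0).

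**4. Sensitivity to the SDs.** If the povidone-iodine SD at that breath is 6 s (sb = 0), pooled variance is (36 + 29 × 16)/30 = 16.67, the SE ratio is 0.816/1.020 = 0.80 and coverage is 88%. If it is 5 s, coverage is 92%. If the other 28 cells have SD 2 s (assumed), pooled variance is (80 + 28 × 4)/30 = 6.4 and coverage is 57%, 66% or 79% for sb = 0, 2, 4. With 8 versus 4 s at all 15 breaths and equal arms, pooled variance is (15 × 64 + 15 × 16)/30 = 40, so at sb = 0 model and true SE are both √(80/50) and coverage is 95%.

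**5. Sensitivity to timing.** Simulation, 4,000 trials per setting: 10%, 20% or 30% of povidone-iodine children pause once for D seconds, with p(1 − p)D² = 48. This gives D = 23.1, 17.3 or 15.1 s. The pause falls at random on one of k breaths; other SD is 4 s; sb is 0, 2 or 4.

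| Breaths over which pauses spread (k) | Model 95% coverage |
|---|---|
| 1 | 81-87% |
| 3 | 89-93% |
| 5 | 92-94% |
| 15 | 94-96% |

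A separate simulation with SD 8 s at one breath, total SD 4 s in every other cell and sb = 2 gave coverage of 81% without a baseline covariate and 79% with one.

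**6. No drug effect.** Per-breath rejection at the 0.33% level was 0.35%, 0.25% and 0.18% for sb = 0, 2, 4.

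**7. What the definition of a response implies.** With 25 breaths the 75th percentile is the 19th ordered value, so at most 6 breaths can exceed it. Counted changes are therefore brief within a child. That does not show that different children respond at the same breath.

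**The case against.** The strongest objection is that the necessary condition is not in the documents. The understatement requires excess variance at the same breath across children, and nothing says so. The 8 versus 4 s pair is a what-if in a power statement about a change score; using it as a residual SD at one of 15 breaths is an assumption. The rule for a change in respiration picks out brief events by construction, and an absence of saline events fits concentrated and scattered responses alike. All of this stands, and it is why the size is given as a range that includes no problem.

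The practical reach is also limited. Under no effect the error rate holds, so an extra rejection is of a false null. The SAP mentions corrected significance and no confidence intervals. The decision changes only in a window of about 1.0 to 1.25 s: of the simulated mean shifts with all pauses at one breath (2.3, 3.5 and 4.5 s), only an observed difference of 3.5 s would change sides. This stands as a limit on severity.

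Finally, the SAP is a short summary in the past tense and may leave out a structure or robust option that was used. That is possible. It would be settled by one added sentence, but it does not change what the text specifies.

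**Conclusion.** The point holds as a conditional statement. The SAP specifies a random subject effect and no residual structure. Fitted that way, the model gives too small a standard error at any breath where povidone-iodine responses concentrate. With 8 versus 4 s at one breath and 4 s elsewhere, the shortfall is 23% to 34% and 95% coverage is 81% to 87%. It is worse if the other breaths are less variable, milder if the excess spread is smaller, and nearly absent if responses spread over five or more breaths. Equal allocation removes it if the excess is the same at every breath. What is at risk is the stated size and certainty of a real effect; the false-positive rate under no effect is not inflated. Confidence is medium, because the documents give neither per-breath SDs nor the timing of responses. A correction is worthwhile because it is cheap and changes little if responses are in fact scattered.

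**What to change.** State the residual covariance structure in the SAP. Keep the same mixed model and use one of the following:

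- Empirical (sandwich) standard errors clustered by subject, with a small-sample correction. In the balanced fit without covariates these equal the Welch standard error; simulated coverage was 94.2-95.7% in every responder setting above.
- The random subject effect plus a diagonal residual variance by breath and arm. Simulated coverage was 94.3-95.4% in five scenarios (1,500 trials each).

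Do not fit an unstructured 15 × 15 matrix per arm: that is 2 × (15 × 16/2) = 240 parameters from about 50 children per arm. As a check, report a Welch comparison of change scores at the administration breath.

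The cost is one re-run on data already collected. The sandwich option adds no variance parameters; the diagonal option has 30 residual variances in place of 1. Intervals will be wider and p-values larger at breaths where responses concentrate. If such a structure was already used, a sentence saying so is enough.

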6.0 Number of Subjects

We will enroll approximately 110 patients in this study to include 55 patients for each randomized ‘treatment’ group. Please refer to section 12.0 for the justification behind this enrollment number.

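### The SAP's >80% power figure belongs to the protocol's single-interval test; neither document gives power for the SAP's 15 Bonferroni-corrected breath comparisons

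*SAP*

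**What the plan says.** **Protocol, section 12.0 (Data Management).** The outcome is the change from the average of five pre-drop intervals to one post-drop interval: "Post-exposure peak to peak interval will only be evaluated as the time between the two peaks at saline or povidone-iodine administration". The groups are compared by linear regression with one treatment effect, and the model "will additionally control for patient age, history of prematurity, and use of any pre-medication". The power statement stands in the same paragraph: 50 per group, variability 4 s, a 2.5 s increase, "using a 2-sided test with significance level set at alpha = 0.05". For variability of 4 s on saline and 8 s on povidone-iodine it adds: "we still have 80% power to detect an increase in the povidone-iodine group of approximately 4 seconds".

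**Protocol, section 6.0.** "We will enroll approximately 110 patients in this study to include 55 patients for each randomized" group.

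**SAP, Statistical Analysis.** The first paragraph repeats the equal-variance calculation with the same inputs, as "power to detect an increase in change in peak to peak interval of 2.5 seconds in the povidone-iodine group". The next paragraph describes a linear mixed model with treatment, breath number, their interaction and a random subject effect, adjusted for "age, pre-term birth, history of apnea, and breath duration prior to drop installation". Then: "Comparisons in breath duration between treatment groups at each of 15 breaths post-drop instillation were estimated from the model using Bonferroni corrected significance". The SAP attributes this model to a plan made beforehand.

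**The concern.** The power figure and the analysis printed after it belong to different tests. The protocol tests one interval once at 0.05. The SAP compares the groups at 15 breaths, each at a stricter level. The covariates differ too: premedication is dropped, and history of apnea and pre-drop breath duration are added. Protocol section 12.0 does not contain the mixed model, and the SAP does not say that its >80% was calculated for something else.

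What is at stake is how a non-significant breath is read. A reader who takes the SAP at face value may judge it against >80% power for 2.5 s and conclude that an effect of that size was probably absent. The calculation does not support that inference at the corrected level.

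**Working it through.** **Inputs.** From the documents: difference 2.5 s; variability 4 s, read as an SD; 50 per group (SAP and protocol 12.0) or 55 (protocol 6.0); two-sided 0.05; 15 comparisons. Assumed: Bonferroni divides by 15; 4 s is the residual SD at a breath; covariates give no gain.

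**Formulas.** SE = SD × √(2/n). Noncentrality = difference / SE. Power = P(T > t_crit), where T is noncentral t with 2n − 2 df. The opposite tail is negligible. Confidence-interval half-width = t_crit × SE.

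**1. The plan's own figure.** n = 50: SE = 4 × √(2/50) = 0.80 s; noncentrality = 2.5/0.80 = 3.125; t_crit (98 df, 0.05) = 1.984; power = 87.2%. The stated >80% is reproduced. With 55 per group it is 90.1%.

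**2. One given breath under the SAP.** Level = 0.05/15 = 0.0033; t_crit (98 df) = 3.009. SE and noncentrality are unchanged.

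| | n = 50, 0.05 | n = 50, 0.0033 | n = 55, 0.05 | n = 55, 0.0033 |
|---|---|---|---|---|
| Power for 2.5 s | 87.2% | 54.8% | 90.1% | 60.9% |
| Detectable with 80% power | 2.26 s | 3.09 s | 2.16 s | 2.94 s |
| Half-width | 1.59 s | 2.41 s | 1.51 s | 2.29 s |

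A mixed-model contrast with variance pooled over 15 breaths has more degrees of freedom. For assumed within-subject correlations of 0 to 0.8 it gives 56–57% with 50 per group and 62–63% with 55, so the choice of model hardly matters here.

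**3. The protocol's unequal-variability case.** n = 50: SE = √(16/50 + 64/50) = 1.265 s, Welch df about 72. Power for 4 s is 88% at 0.05 and 55% at 0.0033. The detectable difference goes from 3.6 s to 4.9 s.

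**4. What a null breath can exclude.** The target is an increase of 2.5 s. If the true difference is zero, the chance that the upper confidence limit lies below +2.5 s equals the power for 2.5 s, by symmetry: 55% for the adjusted interval against 87% unadjusted (n = 50). If the true difference is 0.5 s, use the power for 2.5 − 0.5 = 2.0 s: 31%. If it is 1 s, use the power for 1.5 s: 14%.

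**5. What would raise the 55% (n = 50).**
- Covariates: 80% is reached at a residual SD of 3.24 s or less, that is, if covariates explain about 1 − (3.24/4)² = 34% of the variance.
- Several breaths affected by 2.5 s, success being at least one significant breath: simulation for correlations 0 to 0.8 gives about 72–91% for three affected breaths and 84% to >99% for all 15.
- A model-level test decides: the interaction test with one affected breath has 43% to >99%. The average treatment effect has about 93% or more if all 15 breaths are affected, 11–67% if three are, and 6–13% if one is.

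The documents give no covariate correlation, within-subject correlation or expected duration of effect, so none of these can be chosen over the others.

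**The case against.** The strongest reply is that the SAP never claims >80% power for the 15 comparisons. It presents the figure as a calculation made before the study, prints the inputs including the 0.05 level, and introduces Bonferroni in a later paragraph. A careful reader can see that the level is uncorrected. This stands in part: the figure is a correct design statement, and it would be wrong to infer that the investigators miscalculated. But nothing tells the reader that the figure was for another outcome and model, and no other power figure is offered.

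Second, 55% is one value from a wide range, because it rests on an unprinted divisor, 50 per group, SD 4 s and no covariate gain. The SAP does adjust for pre-drop breath duration and age, which may well reduce the residual SD. This stands, and it is why the figure should be quoted only with its conditions. It does not bring back the >80%, which is not shown to hold at a given breath either.

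Third, with results in hand, the fitted standard errors say more than a planning SD. This also stands, and it makes the adjusted interval the more useful half of the remedy.

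Fourth, the SAP may be referring to a separate plan that contains this model and its power. That cannot be ruled out; the point is limited to the two documents.

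**Conclusion.** The point holds as a minor mismatch between design and analysis. The >80% is right for protocol section 12.0 and does not describe the SAP's breath-level comparisons. With a divisor of 15, residual SD 4 s and no covariate gain, power for 2.5 s at one given breath is about 55% (61% with 55 per group), and the detectable difference rises from about 2.3 s to 3.1 s (2.2 s to 2.9 s).

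A reader might go further in three ways that the documents do not support:
- *The trial as a whole was underpowered.* The 55% concerns one given breath. It is not the chance of finding an effect at any breath or by a model-level test, and the SAP names no single deciding test.
- *A null breath would almost never rule out 2.5 s.* If the true difference is zero, the adjusted interval excludes a 2.5 s increase about 55% of the time. That is well short of 87%, and lower still if a small effect exists, but it is not rare.
- *Positive findings are in doubt.* Bonferroni protects type I error over the 15 comparisons, and a significant breath is not weakened by this point.

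**What to change.** Keep the a priori calculation and add to the SAP, in substance: *This calculation applied to the single interval at drop administration, tested once at two-sided 0.05 (protocol section 12.0). It does not apply to the 15 Bonferroni-corrected comparisons. With 50 per group, SD 4 s, a divisor of 15 and no gain from covariates, power at one given breath is about 55% for 2.5 s, and the difference detectable with 80% power is about 3.1 s.*

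Report each breath contrast with its Bonferroni-adjusted confidence interval, state the divisor, and base the reading of null breaths on that interval rather than on any power figure.

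Do not promote one breath to an uncorrected 0.05 test. The SAP already reports that no child on saline had a change in respiration, so results were known when it was written. If the protocol section 12.0 regression is reported, run it as specified there, including its covariates, and label it as the protocol analysis alongside the corrected comparisons.

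Cost: a short added statement and intervals from the model already fitted, with no new patients or data. The downside is a less favourable stated power.
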